
Study Procedures: Provide a chronological description of the procedures, tests, and interventions that will be implemented during the course of the study. Indicate the number of visits, length of each visit, and the time it would take to undergo the

various tests, procedures, and interventions. If blood or tissue is to be collected, indicate exactly how much in simple terms. Flow diagrams may be used to clarify complex projects.

Research ID. After participants have electronically consented to participate on an Informed Consent document, they will receive the Qualtrics link to complete the Demographic Forms, and Contact Information Forms. Each participant, will then be assigned a Research ID that will be the only identification used on any project data. Because study participants are referred by the Diversion program to distinctly different forms of treatment (either outpatient or residential), the Research ID's will be based on two separate 3-digit series; 100 for participants in outpatient and 200 for participants released from residential. The Research ID will be written on the signed Informed Consent and entered into a Master Link File that will pair the participant name with the Research ID. This file will be kept on password protected laptops used by the RA and Coaches and password protected computers used by the PI and Project Coordinator at the IBR.

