Baseline Survey Administration. After completing the Informed Consent, Demographics Form (e.g., age, gender, race/ethnicity, education level, previous use of telehealth), and Contact Information Form, the participant will receive the Qualtrics link via SMS text or email, to complete the Survey Baseline battery (included in the Appendix). The Qualtrics Survey Baseline assessment battery is completed on a participant's smart phone, hand-held tablet, or PC. The RA will provide the participant with their unique Research ID number, and this will be entered on the first screen by the participant. The Baseline assessment battery consists of forms available on our website (ibr.tcu.edu) and are widely used in substance abuse treatment settings and in our own research. The Baseline battery will also include a measure to gauge chronic pain. The Qualtrics Baseline battery, Demographics Form and Contact Information Form are expected to take up to 1 hour to complete, in addition to the time it takes to complete the Informed Consent administration (estimated at 20 minutes). Following completion of the Qualtrics Survey Baseline assessments, participants will receive an electronic gift card in the amount of \$80. At the end of the meeting, information on the next study meeting will be provided where participants will meet with their assigned Coach. Participants will receive instructions from the RA to (1) access the app on the phone equipment and (2) expect a text message from the Coach to schedule their first telehealth video call. The RA will explain the steps (listed below in "baseline procedures") that the Coach will use to schedule the first telehealth video call. The RA will further explain that the Coach will text message the participant the same day or next business day, except in cases where a participant joins the study on a Friday, in which case the Coach will text message the participant no later than the Monday that follows.

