Qualtrics Survey Mid-Intervention battery (T2). Participants will be contacted in week 5 by the RA to schedule a date and time to complete Mid-Intervention assessments battery in Qualtrics on a smart phone. The Mid-Intervention battery (and follow-up survey battery) repeats the baseline measures. To start the survey, The RA will confirm the unique Research ID number with each participant before sending the Qualtrics survey link, and this will be entered on the first Qualtrics screen. To start the survey, the participant will receive an SMS message with the Qualtrics survey link. At this timepoint in the study (and at follow-up), participants will also be asked to complete the Qualtrics version of the Telehealth Usability Questionnaire (TUQ), a 21-item measure rating the telehealth experience. The Qualtrics Survey Mid-Intervention assessment battery is expected to take 60 minutes to complete. Following completion of the battery, participants will receive an electronic \$40 gift card.

Follow-up surveys (T3). Following the same scheduling procedures used for the Mid-Intervention survey battery, participants will be contacted in week 11 to arrange the Follow-up Survey battery, expected to take 60 minutes to complete. Following completion of the assessments, participants will receive an electronic gift card in the amount of \$40. Following completion of the Qualtrics survey, the RA will contact the participants to thank each for their contributions to the project. All individuals will be invited to participate in an interview with a member of the research team. Our goal is to obtain feedback at the study closeout (Time 3) from a minimum of 6-8 participants. Interested participants may have the Participant Interview Informed Consent administered with the Media Authorization at this time, or the RA will schedule another meeting on a date and time that is convenient for the participant to complete the Informed Consent. The RA will FedEx the signed

documents overnight to the IBR research team and enter the information into the tracking spreadsheet, which is then uploaded to TCU Box for download by authorized project staff.

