The first step in maintaining confidentiality is to assign each participant an arbitrary Research ID that will be used on all data for that participant. A Master Link File will be maintained by the PI, Project Coordinator, Coaches and the field RA that will include the participant's name, Research ID, and study phone number. Treatment Code (described below) will only be included in the Master Link File maintained by the PI and Project Coordinator. This file will be encrypted and stored at the IBR on a secure computer separate from any other participant data. The Master Link File will be password protected, stored electronically, and kept separate from all other data files. It will be accessible only to authorized project staff.

Surveys. The RA will need to have the Master Link File on their TCU-owned secure laptop computer for tracking participants and obtaining Research IDs to enter on project materials. The laptop will be protected by a strong password and the link file, a Microsoft Excel database, will be encrypted and protected by a strong password. Every time a participant comes to complete a survey battery, the RA will use the participant name to look up the Research ID in the database. This will bring up the name and Research ID for that participant. The RA will enter the Research ID on the Qualtrics survey battery or on the paper version alternative. Updated Master Link Files will be uploaded by the RA via TCU Box for download by the IBR authorized researchers (PI or Project Coordinator). Master Link Files will not be stored in a TCU Box folder.

The RA will instruct the participant not to put their name or other identifying information on any paper forms. The Demographics Form—completed only at baseline—includes questions on demographics and background information, and does not have any questions of a sensitive nature. When the participant returns the Demographics Form, it will be mailed to the IBR in an envelope with the Contact Information Form. In the event that the Baseline battery of assessments is completed on paper (this is a back-up option in the event that internet access is not functioning), the survey will be mailed to the IBR in a FedEx envelope, separate from the Demographics Form and Contact Information Form. Data collection on Qualtrics will not have other data that could be used to identify the participant. When

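### The protocol gives conflicting accounts of who enters the 3-digit Research ID that links each survey to a person, and it describes no check of the ID entered; a link carrying the ID would remove the keying step

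*Combined protocol and SAP*

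**What the plan says.** The accounts differ by section and by wave.

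- **Baseline** (Study Procedures, Baseline Survey Administration): "The RA will provide the participant with their unique Research ID number, and this will be entered on the first screen by the participant".
- **Week 6** (Study Procedures, Mid-Intervention battery, T2): "The RA will confirm the unique Research ID number with each participant before sending the Qualtrics survey link". For the entry itself, on the opening screen of the survey, no actor is named. The participant is implied, because the link goes to the participant by text message.
- **Week 12** (Study Procedures, Follow-up surveys, T3): "Following the same scheduling procedures used for the Mid-Intervention survey battery". Only scheduling is carried over; ID entry is not described.
- **All batteries** (Section 16, Surveys): "The RA will enter the Research ID on the Qualtrics survey battery or on the paper version alternative".

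Two further statements determine what an error would do. On format, Study Procedures (Research ID) says "the Research ID's will be based on two separate 3-digit series; 100 for participants in outpatient and 200 for participants released from residential". On other identifiers, Section 16 says "Data collection on Qualtrics will not have other data that could be used to identify the participant". The Research ID paragraph also makes this number the sole identification on project data. No check digit, double entry or comparison of the entered ID with the links sent is described.

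**The concern.** Staff cannot follow both the baseline text and Section 16. The Section 16 wording, in which participants come to complete a battery, reads like an in-person procedure, whereas the opening description rules out in-person contact. Entry by the participant on their own device is therefore the likelier working practice.

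The RA's confirmation at week 6 happens before the ID is typed, so it does not catch a slip on the survey screen. A slip has one of two results. If the typed number was never issued, the survey has no owner until someone traces it. If it belongs to someone else, the answers join the wrong person's record.

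Section 14 needs correct linkage in two places. Self-reported opioid use is compared with drug-test results at each time point (McNemar's test, kappa, sensitivity and specificity), and follow-up scores are compared between intervention completers and non-completers. Misattached surveys would tend to lower agreement and blur group differences. With 40 participants, one survey is 1/40 = 2.5% of a wave.

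**Working it through.** The documents give no error-rate figure, so there is nothing of theirs to reproduce. The calculation below is a scenario.

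**Inputs from the documents**
- 40 participants (Section 11) and three batteries (Section 16), so at most 40 × 3 = 120 ID entries.
- Three-digit IDs in a 100 series and a 200 series (Study Procedures, Research ID).

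**Assumptions not in the documents**
- A keying error rate *e* of 1% or 2% per entry, each error being one wrong digit.
- A 20/20 split between the series, with IDs either consecutive or scattered at random within each series. Section 13 calls the ID random and Section 16 calls it arbitrary, but the issuing rule is not given.

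**Step 1. Share *c* of one-digit errors that hit another issued ID.** Each ID has 3 × 9 = 27 one-digit substitutions, so 40 IDs have 1,080.
- Consecutive from 101 and 201: 404/1,080 = 37%.
- Consecutive from 100 and 200: 440/1,080 = 41%.
- Extreme case, all 40 in one consecutive series: 43–44%.
- Scattered within each series: about 13% on average (range 10–18% over 2,000 random draws).

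**Step 2. Keying errors of any kind over 120 entries.** Expected number = 120*e*; chance of at least one = 1 − (1 − *e*)^120.
- *e* = 1%: 1.2 expected; 1 − 0.99^120 = 70%.
- *e* = 2%: 2.4 expected; 1 − 0.98^120 = 91%.

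**Step 3. Surveys attached to the wrong participant.** Expected number = 120*ec*; chance of at least one = 1 − (1 − *ec*)^120.

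| IDs | *e* | Expected | Chance of at least one |
|---|---|---|---|
| Scattered, *c* = 0.13 | 1% | 0.16 | 1 − (1 − 0.0013)^120 = 14% |
| Scattered, *c* = 0.13 | 2% | 0.31 | 1 − (1 − 0.0026)^120 = 27% |
| Consecutive, *c* = 0.37 | 1% | 0.44 | 1 − (1 − 0.0037)^120 = 36% |
| Consecutive, *c* = 0.37 | 2% | 0.89 | 1 − (1 − 0.0074)^120 = 59% |

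**Step 4. Baseline only.** Participant entry is explicit only at baseline, so the same formula with 40 entries gives the narrowest reading.
- Scattered: 1 − (1 − 0.0013)^40 = 5% to 1 − (1 − 0.0026)^40 = 10%.
- Consecutive: 1 − (1 − 0.0037)^40 = 14% to 1 − (1 − 0.0074)^40 = 26%.

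None of these figures takes credit for the week-6 confirmation or for later detection.

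**The case against.** The strongest reply is that most slips would come to light.

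- A typed ID that was never issued is visible as such.
- A slip onto an issued ID produces a duplicate if the true owner also completes that wave, and leaves a gap for the sender.
- Links go to individually scheduled participants and a gift card follows each completed battery, so staff must know who has finished.

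This stands as a reason to expect fewer lasting errors than the table shows. It does not settle the matter, because the plan does not describe anyone making the comparison.

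Much of Aim 1 is also unaffected. App utilization and session-satisfaction data arrive under the phone number and are recoded by the Project Coordinator, and provider data arrive under a separate Treatment Code. Overall distributions of the usability questionnaire do not change if IDs are swapped. That stands too: the exposure lies in the person-level comparisons.

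A reader might infer several stronger points that the documents do not support.

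- **Participants key the ID at every wave.** This is explicit only at baseline.
- **A first-digit slip moves the person between outpatient and residential.** Only 1 of the 9 possible first-digit substitutions switches series; the other eight give a number outside both. Level of care is also reported separately on the provider form.
- **A planned comparison by treatment setting is corrupted.** Aim 2 contains no such comparison.
- **An ID-carrying link removes all error at no cost.** It removes keying, but the RA can still send a link to the wrong person, and such a link always carries an issued ID. The documents do not address link capability or cost.

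**Conclusion.** The point holds as a minor data-linkage weakness. The accounts of ID entry conflict between Study Procedures and Section 16, the survey has no second identifier, and no check of the entered ID is described.

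If participants key the ID at all three waves at an assumed 1–2% error rate, the chance of at least one wrong-owner survey lies between about 14% and 59%, depending mainly on how IDs are issued. Because the documents call the IDs random or arbitrary, the lower range of 14–27% deserves at least as much weight as the consecutive-numbering range of 36–59%. The expected number of such surveys is below one in every scenario tabulated, before any detection.

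The conflict needs correcting whatever the true error rate. No sample-size, power or alpha figure depends on it.

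**What to change.** Replace the three accounts (Baseline Survey Administration, the T2 paragraph, and Surveys in Section 16) with one rule covering baseline, week 6 and week 12, and state it for T3 as well.

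- **Preferred:** send each participant an individual survey link for each wave, with the Research ID stored as a hidden field so that nobody types it.
- **If that is not available:** check every entered ID against the RA's record of links sent before the file is downloaded, and resolve duplicates, gaps and unissued numbers then. The timing matters because the protocol does not keep data on the survey server after download.
- **Paper back-up:** keep manual entry of the ID for this route only.

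The cost is a wording change and a small set-up task; the RA already tracks participants and sends the survey links at week 6. With the preferred option, participant-keyed entries fall from at most 120 to 0. The remaining risk is a link sent to the wrong person, for which the documents give no rate, so the RA must still match each link to its recipient.

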Informed Consent document; an \$80 e-gift card for the time to complete intake surveys at the start of the study and \$40 e-gift cards for completing assessments at week 6 (the midpoint) and week 12 (the end of the intervention period) during the 3-month study (eligible for up to \$160) in the form of electronic gift cards to online merchants (e.g., Walmart, Amazon). Participants who use their own smartphone will get a \$25 electronic gift card each month they participate in the study for messaging and data charges (a total of \$75 for 3 months). Participants will not be responsible for any costs to participate in this study. The *Participant Interview Informed Consent* document will indicate that compensation is a \$20 electronic gift card for completing a scheduled interview with a member of the research team. Participants who volunteer to be interviewed at the end of the study will be contacted by the RA to schedule a virtual interview. Both Consent documents will also have information indicating that participation or lack of participation will not affect the individual's status in the ODP, treatment, or treatment status in any possible way. Therefore, participation will be strictly voluntary and should clients choose not to participate or withdraw from the study at a later time, they may do so without repercussion. Participants can withdraw from the study by contacting the RA or Coach by phone and stating that they wish to stop participating. In cases where the Coach is contacted, the Coach will relay the decision to the RA for administrative purposes. The Consent will explain that the research-issued smart phone equipment will be collected by the RA at a time to be arranged with the participant. The Informed Consents will also describe the confidentiality assurances and the procedures employed to safeguard the data. In particular, it will be explained that information collected will be identified only by a random participant **Research ID** number and research reports will only be in aggregate form, whereby no individual can be identified. Recorded interviews will be redacted and identified only by the Research ID for tracking purposes. No individual data (survey, agency, or recorded opinions) will be reported to the ODP authorities or any other entity. The *Primary Study Informed Consent* will include language to allow release of behavioral healthcare agency data from the substance use treatment provider (providing services as part of the Opioid Diversion Program) to the research team for tracking participants across the 12-week intervention, thus providing treatment performance indicators. The *Primary Study Informed Consent* will also state that behavioral healthcare data will be requested by the research team using a variation of the Research ID (referred to as the **Treatment Code**) to link data to a participant. The Treatment Code is an arbitrary number assigned to each participant by the research team. The Code will be provided to the behavioral healthcare provider in a file that links the Code to the participant's name. Therefore, data requests from the research team will include only the Treatment Code, which providers will use to identify the client from the linking file. Behavioral healthcare providers will use only the Treatment Code in submitting data to the research team. Behavioral agency data will be shared with the research team via upload to TCU Box, a secure online data sharing platform. After an Informed Consent has been administered, the RA will answer questions and the client will then be asked to provide written consent.

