Baseline procedures. The RA will describe the participant's options for phone equipment. In the event that the participant chooses to use their own phone for the study, the RA will assist the participant with downloading the T-CAP app. Participants who choose to use a study-issued phone will receive a FedEx delivered smart phone with the T-CAP app pre-loaded and instructions for use. For participants who choose to use their own phone equipment, the study will reimburse in the amount of \$25 (in the form of an electronic gift card) per month to participants who are engaged in the entire 12-week intervention. For participants who opt to use the research smart phone equipment, phones will be on an unlimited plan maintained through the IBR.

After the phone equipment decision is made by the participant, the RA will document (in the participant tracking spreadsheet) the date, whether the phone is owned or research-issued, phone number, and the phone FCC ID number for each participant. In the event that a participant loses a research-issued phone, the participant will be advised by the RA, that the project will provide 1 replacement phone. In the event that a participant loses their own phone, they can request a research-issued phone or if they obtain another phone of their own, the same reimbursement at end-of-study will apply. Participants can arrange for a replacement phone by emailing or calling the T-CAP RA at the contact information on the T-CAP Flier, included with the participant's copy of the Consent document. In the event that a participant does not have access to email or a borrowed phone, they can contact the RA through the Lake County Health Department.

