Completed Provider Data Request Forms will be uploaded by the provider to TCU Box and available for download by authorized project staff. Data from the forms will be entered into a provider data tracking Microsoft Excel file at the IBR and maintained on a secure server at the IBR office.

14. Data Analyses: Describe how you will analyze your data to answer the study question

Aim 1: Demonstrate intervention feasibility by measuring study participant receptivity and utilization of the telehealth approach. Feasibility will be primarily assessed by descriptive analyses of participation, satisfaction, and telehealth usability data. We will examine distributions on these measures as well as characteristics of participants with high and low participation sample size, we will be more interested in trends than in statistical significance. Receptivity and utilization will be assessed by self-report measures as well as participation data from the T-CAP app. Self-report measures will include the Telehealth Usability Questionnaire (TUQ), Telehealth Session surveys, and semi-structured closeout interviews. The TUQ gauges constructs that are consistent with those in the telehealth literature and include: Usefulness, Ease of Use Interaction Quality, Satisfaction and Future Use, Interface Quality; and Reliability. TUQ scores of 4.0 (agree) and above on each domain indicate high receptivity. Scores below 4.0 will be interpreted as an indication that the participant encountered some challenge in that area of using the telehealth system. Data from the TCAP app will provide evidence of utilization (i.e., process data on session completion, duration, and number of unscheduled contacts). Two satisfaction questions are asked after each video conferencing session. We will primarily examine counts and distributions of these data but will also examine characteristics of participants with high and low levels of participation. All individuals will be invited to participate in an interview with a member of the research team. Our goal is to obtain feedback at the study closeout (Time 3) from a minimum of 6-8 participants. Drawing on our extensive qualitative experience, a semi-structured interview with questions from the TUQ, paired with relevant probes, will guide the interview to help us gain a better understanding about how the telehealth experience impacted participants.

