Aim 2: Evaluate the proposed T-CAP measures to assess their performance in gauging the impact of telehealth on initiation of in-person Substance Use (SU) treatment, short-term retention in referred SU treatment, and access to other appropriate treatment services (e.g., MAT). Our multidimensional approach includes data from self-report attendance and treatment engagement, self-report drug use, Coaches' advocate records on number of completed assertive referrals, and agency records from police and BH providers (including intake and during-program UA test results). In order to examine groups differences for intervention completers (C) vs non-completers (NC) (i.e., individuals who do not complete the 7 coaching video calls), group differences using t-tests and chi-square tests and we will estimate effect sizes needed for determining a sample size for a future R01 proposal. To assess potential assignment bias, we will test to see if there are baseline differences in demographics: participant race, gender, age and other demographic characteristics, as well as baseline measures of opioid use frequency and amount will be examined using chi-square and t-tests. Effect sizes will be computed for group differences on multiple outcomes (treatment initiation, retention, referrals to expanded SU service options, missed appointments). Service attendance records will be corroborated monthly with service provider records. Examinations of referrals to MAT and alternative pain management care between the C and NC groups, utilizing agency records data and the Coach tracking, will be conducted using a z-score to test differences in proportions of referral types. This will be calculated for all assertive referrals (resulting in scheduled appointments) collectively for a participant, as well as for different types of services.

Analyses of Secondary outcomes. We will examine differences between C and NC groups on several secondary outcomes. Analyses will typically involve t-tests, chi-square tests, and correlations. For example, we will use t-tests to assess differences between groups on the 3-month follow-up measures

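### Own-phone reimbursement is stated under two different rules, and one makes up to $75 depend on staying all 12 weeks

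*Combined protocol and SAP*

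**What the plan says.** Item 13 (Consenting Procedure), where it sets out what the primary consent will explain, gives own-phone users a $25 "electronic gift card each month they participate in the study for messaging and data charges", with a stated total of $75 over 3 months. It adds: "Participants will not be responsible for any costs to participate in this study". The same item says that people may withdraw later without repercussion.

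The Baseline procedures paragraph under Study Procedures describes the same $25, but as payable "per month to participants who are engaged in the entire 12-week intervention". Further on, for a participant who loses their own phone and obtains another of their own, it says that "the same reimbursement at end-of-study will apply". For those who take a study-issued phone, "phones will be on an unlimited plan maintained through the IBR"; no condition on staying in the study is attached. The participant chooses between the two, and the tracking spreadsheet records which was chosen.

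Item 14 (Data Analyses) uses call completion twice. Under Aim 1, evidence of utilisation from the app is "process data on session completion, duration, and number of unscheduled contacts". Under Aim 2, and for the secondary outcomes, completers are compared with non-completers, the latter being "individuals who do not complete the 7 coaching video calls". The Scheduled Telehealth Sessions paragraph places the seventh call in week 12. Item 14 does not mention phone type.

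**The concern.** The two descriptions cannot both be operated. One accrues month by month. The other, taken at its word, pays only those who stay to the end. Nothing elsewhere in the document says which governs.

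Two things are at stake. The first is the undertaking to participants. The money is described as covering messaging and data charges, so a person who leaves early under the Baseline procedures rule would carry charges already incurred, despite the statement that taking part costs nothing. Item 15 names perceived coercion as a risk in this police-diversion population, so a payment forfeited on leaving should not be there by accident.

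The second is interpretation. Under the Baseline procedures rule, one self-selected subgroup has a payment tied to staying for 12 weeks, the same span over which the seven calls are delivered. That could affect how many calls these participants complete, and so both an Aim 1 measure and membership of the Aim 2 groups.

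**Working it through.** **Inputs.** From item 13: $25 per month, $75 in total over 3 months; assessment payments of $80 at baseline, $40 at week 6 and $40 at week 12. From Baseline procedures: $25 per month, limited to those engaged for the entire 12 weeks. I treat the end of month 3 as week 12.

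**Step 1: reproduce the stated totals.** 25 × 3 = $75, as item 13 states. 80 + 40 + 40 = $160, also as stated.

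**Step 2: tabulate the two rules for own-phone users.** With *m* completed months, item 13 pays 25 × *m*. Baseline procedures, read literally, pays 75 if *m* = 3 and 0 otherwise.

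| Months completed | Item 13 | Baseline procedures | Difference |
|---|---|---|---|
| 0 | $0 | $0 | $0 |
| 1 | $25 | $0 | $25 |
| 2 | $50 | $0 | $50 |
| 3 | $75 | $75 | $0 |

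The rules coincide only at zero months and at full term.

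**Step 3: the amount that depends on staying.** An own-phone user can receive at most 160 + 75 = $235 from the primary study. Under the Baseline procedures rule, 75 / 235 = 32% of that depends on staying 12 weeks. This is a gross share. The documents give no figure for what own-phone users spend on data, so a net incentive cannot be derived.

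**Step 4: possible effect on completion.** This cannot be computed, because the documents give neither the share of own-phone users nor a completion rate. To show the scale only, assume 60% completion on study phones, an own-phone share *s* of 25% to 75%, and completion higher by *u* = 5 to 20 percentage points on own phones. Overall completion then rises by *s* × *u*:

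- lowest: 0.25 × 0.05 = 0.0125, about 1 point;
- highest: 0.75 × 0.20 = 0.15, or 15 points.

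At *s* = 50% and *u* = 10 points, overall completion is 0.5 × 0.70 + 0.5 × 0.60 = 65%. Own-phone users are then 0.35 / 0.65 = 54% of completers and 0.15 / 0.35 = 43% of non-completers. Every input in this step is assumed. It shows what a given uplift would do, not that there would be one.

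**The case against.** The best defence is that the Baseline procedures sentence is loosely worded: it still says per month, and may only describe what a full-term participant receives. The end-of-study phrase in the same section makes that reading harder to sustain. Even if it is what was meant, the text needs correcting.

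A reader might go further and infer that the protocol pays own-phone users to achieve the utilisation outcome, and that completer status is therefore confounded with phone ownership. The documents do not support that, for four reasons.

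- Being engaged is not defined. Someone could stay in contact for 12 weeks, miss one call, be paid, and still count as a non-completer.
- Session completion is one of three app utilisation measures, and Aim 1 also rests on the usability questionnaire, the session satisfaction questions and interviews.
- The payment is a cost offset. Study-phone users have the equivalent covered in kind through the unlimited plan, so it is not simply a bonus that they lack.
- Phone type is self-chosen and might be related to completion under either rule. The completer comparison is itself non-randomised, in a 40-person feasibility study that puts trends ahead of significance.

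These points stand and limit the argument about interpretation. They do not remove the contradiction between the two rules or the conflict with the no-cost statement.

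The consent form itself is not in the copy reviewed, so item 13 is evidence of what it is meant to say, not of its final wording.

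**Conclusion.** The inconsistency is real and minor. For an own-phone participant who leaves early, the two rules differ by $25 after one completed month and by $50 after two. This rests on a literal reading of the Baseline procedures text, which its end-of-study wording supports. That rule also conflicts with the statement that participants bear no costs.

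On interpretation, the supportable conclusion is limited: the rule makes up to $75 depend on remaining for 12 weeks, for own-phone users only, and this may influence session completion and completer status. Neither the existence nor the size of such an effect can be established from the documents. With no control arm, what could be affected is the feasibility estimate and the completer comparison, including the effect sizes intended for the future R01 proposal; no randomised contrast is involved.

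**What to change.** 1. Reconcile Baseline procedures with item 13 and with the actual consent wording, so that the $25 accrues for each month of participation and does not depend on staying the full 12 weeks. Remove the entire-12-week and end-of-study conditions.
2. State what counts as participating in a month and how a partial month is treated. Item 13 is silent on both.
3. Report call completion descriptively by phone type. The tracking spreadsheet already holds this, so no new data are needed. With 40 participants, a table of counts is enough.
4. If payments have already been made, state which rule was applied.

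The cost is a short wording amendment plus, relative to the literal Baseline procedures rule, up to $50 for each own-phone participant who stops early, or up to $75 if a partial third month is paid. In the extreme case that all 40 used their own phones and all stopped early, that is 40 × 50 = $2,000, or 40 × 75 = $3,000.
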